2.6.2. On-Treatment Observation Period

This observation period includes data from the day of the **first dose of study drug to 2 days after the last dose of the study drug, inclusively** (dose dates defined in Section 2.5).

All randomized subjects will be included in the On-Treatment observation period. A conservative approach will be used for subjects who were randomized but never dosed to include any event that may occur even if the subject did not take study drug. This is defined to include VTE-related events that occur during the study even if the subject had not taken study drug. Only those events that occur prior to the double-blind period end date will be included in the on-treatment observation period.

Event: All efficacy and safety events (with respect to deaths, *VTE-related deaths are counted as events for primary efficacy composite endpoint. For Bleeding related deaths, major bleeding is counted as events for the primary safety endpoint*) that occurred from the date of first dose of study drug up to the last dose of study drug+2 days will be included in the analysis of the On-Treatment observation period.

- Event time - The time to event is defined as the time from first dose date to the time of the first event during this observation period.
 - For randomized subjects but never dosed: The time to event will be defined as the time from randomization to the time of the event during the time in study. This imputation rule will be applied only for the ITT population.

Censoring: Subjects who do not experience an event during this observation period will be censored.

Subjects who died during this observation period will be censored as of their death date for endpoint analysis not related to death.

- Censoring time - The time to censoring is defined as the time from first dose date to the minimum (earliest) of (last dose date+2 days, death date).
 - For randomized subjects but never dosed the time to censoring will be defined as the time from randomization to the minimum of (last day of their complete assessment for study outcomes during the double-blind period [double-blind completion/withdrawal], death date [non VTE-related deaths for primary efficacy composite endpoint]).

2.6.3. Post-Randomization Observation Period

This observation period includes all data from randomization to Day 210/EOS.

Specifically, this observation period will include all events that have occurred after randomization through Day 210/EOS inclusive of all events after completion of double-blind period/Day 180 through Day 210 as well as all events that occurred after subject had withdrew early from the double-blind period through Day 210.

Event: All efficacy events (with respect to deaths, *VTE-related deaths are counted as events for primary efficacy composite endpoint*) that occurred from the date of randomization up to the Day 210/End-of-Study [EOS] (defined in Section 2.5) will be included in the analysis of the Post-Randomization observation period.

- Event time - The time to event is defined as the time from randomization to the time of the first event during this observation period.

Censoring: Subjects who do not experience an event during this observation period will be censored.

Subjects who died during this observation period will be censored as of their death date for endpoint analysis not related to death.

- Censoring time - The time to censoring will be time from randomization to the minimum of (last contact date [up to and including the Day 210 = EOS date defined in Section 2.5], death date [non VTE-related deaths]).

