1.2.1. Study Drug Discontinuation and Early Withdrawal from Double-Blind Period

As per the protocol (Section 10.2.2), if a subject permanently discontinued study drug before the Day 180 visit/End of double-blind (EODB) period, this would not result in automatic permanent withdrawal of the subject from the study. Subjects are encouraged to make every effort to continue participation in the study and complete the schedule subsequent study visits until the planned end of their study double-blind duration (Day 180/EODB). All outcomes/events data (VTE, vital status (alive/dead), MI, stroke, and other thrombosis events) and safety data (including bleeding events) are collected. If a subject permanently discontinued study drug prior to Day 180 but continued in the study and completed all study visits up to Day 180, then this subject is considered as having ‘completed the double-blind period’ (that is, participated in the study up to the Day 180 visit).

All subjects including those who discontinued prior to Day 180 visit are contacted by telephone for a Day 210/EOS follow-up assessment. Any outcome/event data (including vital status) reported during this telephone visit is collected at this Day 210/EOS visit as agreed upon by the subject informed consent. In the event a subject withdrew consent or is lost-to-follow up, the vital status data are obtained through public information (death and other registries) per local guidelines and as allowed by local registration.

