2.5. Definition of Study Dates and Observation Period End Dates

The study dates and period end dates will be used to define the time period for data included in the analysis of efficacy and safety endpoints for the different observation periods (defined in Section 2.6).

Study Day 1 date: the date of randomization of the subject.

End-of-Study (EOS): the date of the last study-related procedure for the subject (EOS is defined as last assessment day during the study, including the Day 210/Post-Treatment Follow Up visit) and is defined as the minimum (last assessment day during the study, death date).

Double-Blind period start date will be the date of randomization.

Double-Blind period end date will be defined as the completion/early withdrawal date (date of completion or early withdrawal [any reason including death] from the double-blind period).

Up-to-Day 180 observation period end date will be defined as follows;

- Day 180/EODB completion date (for subjects who completed the double-blind period) or
- Death date (subjects who died during the double-blind period [DB reason=death] or during any time from randomization through Day 180 [died post withdrawal from DB but before Day 180/EODB visit] or
- Maximum (double-blind withdrawal date, randomization date + 180 days) for subjects who withdrew early from the double-blind period [any reason other than death] and had not died during the time from randomization through Day 180

First dose date: the date on which the first dose of study drug is taken by the subject. If missing or partial for a subject who takes study drug, the first dose date is set to the randomization date.

Last dose date: the date on which the last dose of study drug is taken by the subject (dose end date). If the dose end date is missing or partial for a subject who takes study drug, the last dose date is set as follows

- Maximum (Minimum (discontinuation date in the double-blind period [including death date during double-blind period], last visit date when drug is dispensed + number of pills dispensed - number of pills returned at following visit), imputed partial last dose date, exposure start date of last record))
 - Imputation rule for partial dates: If only the day is missing, then day imputed to the last day of that month. If day and month are missing, the date will be imputed to the start date if year is the same, else imputed to January 1st.

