2.6.1. Up-to-Day-180 Observation Period

This observation period includes data from randomization to Up-to-Day 180 end date (defined in Section 2.5).

Event: All efficacy events (with respect to deaths, *VTE-related deaths are counted as events for primary efficacy endpoint. For the secondary efficacy endpoints, all-cause deaths are counted as events*) that occurred from randomization through the Up-to-Day 180 end date (Section 2.5) will be included in the analysis of this observation period.

- Event time - The time to event is defined as the time from randomization to the time of the first event during this observation period.

Censoring: Subjects who did not experience an event during this observation period will be censored at the last day of their complete assessment for study outcomes.

Subjects who died during this observation period will be censored as of their death date for endpoint analyses not related to death.

- Censoring time - The time to censoring is defined as the time from randomization to the minimum of (last day of their complete assessment for study outcomes during the double-blind period [double-blind completion/withdrawal], death date [non VTE-related deaths for primary efficacy composite endpoint]).

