2.6.4. Post-First Dose Observation Period

This observation period includes all data from the first dose of study drug to Day 210/EOS.

Specifically, this observation period will include all events that have occurred after first dose through Day 210 inclusive of all events after double-blind period completion/Day 180 through Day 210 as well as all events that occurred after subject had withdrew early from the double-blind period through Day 210.

All randomized subjects will be included and the imputation rule for event times for randomized subjects but never dosed described in Section 2.6.2 will also be applied for the analysis of data for this observation period. All events that occur prior to the End-of-Study date will be included in the post-first dose observation period.

Event: All efficacy events (with respect to deaths, *VTE-related deaths are counted as events for primary efficacy composite endpoint*) that occurred from the date of first dose up to the Day 210/End-of-Study[EOS] (Section 2.5) will be included in the analysis of the Post-First Dose observation period.

- Event time - The time to event is defined as the time from first dose date to the time of the first event during this observation period.
 - For randomized subjects but never dosed: The time to event will be defined as the time from randomization to the time of the event during the time in study. This imputation rule will be applied only for the ITT population.

Censoring: Subjects who do not experience an event during this observation period will be censored.

Subjects who died during this observation period will be censored as of their death date for endpoint analysis not related to death.

- Censoring time - The time to censoring is defined as the time from first dose date to the minimum (earliest) of (last contact date [up to and including Day 210 visit date = EOS date defined in Section 2.5], death date [non VTE-related deaths])
 - For randomized subjects but never dosed: The time to censoring will be defined as the time from randomization to the minimum of (last contact date [up to and including Day 210=EOS date, death date [non VTE-related deaths]]).

Examples are illustrated in Figures in the Appendix.

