5.2.5.2. Sensitivity Analysis for Primary Efficacy Composite Endpoint

In this study, all data regarding occurrence of DVT, PE events and vital status (alive/dead) events will be collected for all subjects (completers and early withdrawal) at the Day 210/follow-up visit. Data for the primary efficacy composite endpoint will be missing for subjects for whom the Day 210/follow-up visit is not performed or if the visit was performed but the occurrence of an event was reported as unknown. A conservative approach will be used for subjects who withdrew from the double-blind period and did not have an event during the double-blind period.

In this approach, subjects who withdrew from the double-blind period for any reason other than death and were censored (i.e. had not experienced any VTE-related primary efficacy event during the double-blind period) and have missing or unknown Day210/follow up status will be considered as having a VTE-related event (i.e. not censored). The time from randomization to time of withdrawal will be assumed to be the time to an occurrence of a VTE-related primary efficacy composite event (no specific individual component will be assigned as the worst case).

The sensitivity analysis for the primary efficacy composite endpoint will be based on the '**Up-to-Day 180**' observation period for the ITT analysis population. For the above sensitivity analyses, the cumulative distribution function of the time to first occurrence will be estimated by the Kaplan-Meier method and tested using a log-rank test, stratified by tumor type (APC or non-APC).

The estimate of the hazard ratio (HR), RRR (RRR=100*[1-HR] %) and the 95% confidence intervals for the treatment effect will be provided based on a stratified Cox proportional hazard model (stratification factor: APC or non-APC) and including treatment group as a binary covariate (i.e., rivaroxaban, placebo).

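### The two supportive analyses to Day 210 censor at last contact even when VTE status at that contact is unknown, so some early withdrawals are credited with unobserved event-free time

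*SAP*

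**What the plan says.** SAP Section 2.6.3 (Post-Randomization) sets the censoring time for a subject without an event at the earlier of non-VTE death and the "last contact date [up to and including the Day 210 = EOS date defined in Section 2.5". Section 2.6.4 (Post-First Dose) counts from first dose but uses the same limit, "last contact date [up to and including Day 210 visit date = EOS date defined in Section 2.5", and repeats it in the sub-bullet for subjects never dosed. Section 2.5 adds no condition on outcome status: "EOS is defined as last assessment day during the study, including the Day 210/Post-Treatment Follow Up visit".

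Two other sections treat the same situation differently:

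- Section 5.2.5.2 regards primary endpoint data as "missing for subjects for whom the Day 210/follow-up visit is not performed", and also "if the visit was performed but the occurrence of an event was reported as unknown".
- Section 2.6.1 (Up-to-Day 180) says that subjects without an event "will be censored at the last day of their complete assessment for study outcomes". Section 4.6 applies this to early withdrawals by using the double-blind withdrawal date.

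Section 1.2.1 explains how the situation can arise. All subjects, including those who stopped early, are "contacted by telephone for a Day 210/EOS follow-up assessment". After consent withdrawal or loss to follow-up, "the vital status data are obtained through public information (death and other registries".

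**The concern.** Censoring in a VTE analysis should fall where the subject was last known to be free of VTE. Under 2.6.3 and 2.6.4 it falls where the subject was last reached, whether or not anything was learned about VTE. A subject whose outcome 5.2.5.2 would call missing stays in the risk set as event-free through Day 210.

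Time in which no event could have been recorded enlarges the denominators and pulls down the cumulative event curves that Section 5.2.3 requires to be displayed. If such subjects are more common, or withdraw earlier, in one arm, that arm looks better and the hazard ratio shifts in its favour. Section 5.2.3 presents these analyses as checks on the robustness of the primary result, so they should not treat unknown outcomes as favourable ones. The missing-status analysis in 5.2.5.2 does not repair this, because it covers the Up-to-Day 180 period only.

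**Working it through.** **The three rules applied to one subject.** Withdrawal on Day 60 without an event; Day 210 contact made; VTE status unknown.

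- Section 2.6.1: censored at the last complete outcome assessment, about Day 60.
- Section 5.2.5.2: outcome missing; imputed as an event at withdrawal.
- Sections 2.6.3 and 2.6.4: censored event-free at Day 210. Credited time is 210 − 60 = 150 days.

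For a subject who completed the double-blind period on Day 180, the most that can be credited is 210 − 180 = 30 days.

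**Inputs from SAP Section 1.4.** 180-day event rates of 14.5% (placebo) and 6.0% (rivaroxaban); 20% dropout; 350 per arm. The SAP gives no figure on this point. Its design figure does reproduce: 350 × 0.8 = 280 per arm gives 91.5% power by the two-proportion normal approximation, in line with the stated >90%. It is not in dispute.

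**Assumptions, not in the SAP.** Exponential event and withdrawal times; withdrawal of 20%, or 40% as a high case; and u, the share of withdrawals reached at Day 210 with VTE status unknown. The other withdrawals are censored at withdrawal. Those with known status at Day 210 would in fact add genuine follow-up, which would make the effect somewhat smaller.

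**Correct Day 210 rates (u = 0).** Constant hazard gives 1 − (1 − p)^(210/180):

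- placebo 1 − 0.855^(7/6) = 16.7%
- rivaroxaban 1 − 0.94^(7/6) = 7.0% (6.95% in the simulation)

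**Upper limit (u = 100%, 20% withdrawal).** Nobody leaves the risk set at withdrawal, so the Kaplan-Meier estimate equals the proportion with a recorded event. With a = −ln(1 − p) and w = −ln(0.8) = 0.2231, this is

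a/(a + w) × [1 − 0.8(1 − p)] + 0.8(1 − p) × [1 − (1 − p)^(1/6)]

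- placebo: 0.4125 × 0.316 + 0.684 × 0.02577 = 14.8%
- rivaroxaban: 0.2171 × 0.248 + 0.752 × 0.01026 = 6.2%

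**Intermediate cases** (simulation, 2 million subjects per arm, u equal in both arms):

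| Withdrawal | u | Day 210 rate, placebo / rivaroxaban | Rate ratio | Credited share of placebo person-time |
|---|---|---|---|---|
| 20% | 0 | 16.69% / 6.95% | 0.394 | 0 |
| 20% | 25% | 16.15% / 6.72% | 0.395 | 3.3% |
| 20% | 50% | 15.66% / 6.51% | 0.395 | 6.4% |
| 20% | 100% | 14.79% / 6.15% | 0.395 | 12.1% |
| 40% | 50% | 14.35% / 5.96% | 0.395 | 14.2% |
| 40% | 100% | 12.75% / 5.28% | 0.396 | 24.9% |

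Mean credited time per affected placebo subject is 126 days at 20% withdrawal and 130 days at 40%.

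**Unequal shares.** The rate ratio (events over person-time) stands in for the hazard ratio.

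| Withdrawal | u placebo | u rivaroxaban | Rate ratio |
|---|---|---|---|
| 20% | 25% | 50% | 0.382 |
| 20% | 50% | 25% | 0.408 |
| 40% | 25% | 50% | 0.367 |
| 40% | 50% | 25% | 0.425 |

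Against 0.395, that is about ±3% at 20% withdrawal and ±7 to 8% at 40%.

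**Scale.** With 350 per arm and 20% withdrawal, about 64 events are expected by Day 180, some 45 placebo and 19 rivaroxaban. SE(log HR) ≈ √(1/45 + 1/19) = 0.27. The shift from 0.395 to 0.408 is ln(0.408/0.395) = 0.032, about one-eighth of a standard error; 0.425 is about one-quarter.

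**The case against.** - **Narrow reach.** Only two of the five supportive analyses in Section 5.2.3 are touched, and nothing in the Section 5.5 hierarchy depends on them. This stands. A reader might infer that the primary result is compromised. The SAP does not support that: the primary, key secondary, sensitivity and competing-risk analyses all use the Up-to-Day 180 period, which censors at the last complete outcome assessment.
- **Few subjects may be exposed.** Day 210 is meant to collect outcomes as well as vital status, and a subject with a known absence of events is properly at risk until then. If the visit did not happen, last contact is earlier and little is over-credited. This also stands. It would be wrong to infer that every early withdrawal gains months; the clear case is a performed visit with unknown status. Registry checks are less certain: the SAP ties the limit to a study procedure but does not expressly exclude them.
- **Unsupported inputs and small effect.** The SAP gives no unknown share, and at 20% withdrawal u = 50% already supposes that half of all dropouts were reached without an answer. The shifts are small against the standard error. Both are correct. Nor does the SAP show that unknown status would differ by arm in this blinded trial, so a claim of bias towards rivaroxaban, or towards placebo, is unsupported.
- **The remedy is partial.** Day 210 is a telephone contact, whereas asymptomatic proximal DVT is sought by ultrasound. Even a known status by telephone does not cover unscreened asymptomatic events. True, but this is a further limitation and no reason to count unknown status as event-free.
- **Material not shown.** The attachment figures and the separate data presentation specifications might define last contact more tightly. That cannot be checked, and the text as written does not.

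**Conclusion.** The concern holds for two supportive analyses. As written, 2.6.3 and 2.6.4 count as event-free follow-up what 5.2.5.2 calls missing, and they drop the safeguard in 2.6.1. The time credited can reach several months for an early withdrawal whose Day 210 visit took place with VTE status unknown, and at most about 30 days for a double-blind completer.

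The certain effect, if any such subjects exist, is lower Kaplan-Meier rates. At 20% withdrawal the Day 210 placebo rate falls by about 0.5 percentage points if a quarter of withdrawals are affected and by about 1 point if half are. The hazard ratio is practically unchanged when shares and timing are equal between arms. It shifts by about 3% at 20% withdrawal, or 7 to 8% at 40%, if one arm has twice the unknown share of the other (50% against 25%), in either direction. All these sizes rest on assumed shares and exponential times. The point is worth correcting but does not bear on the confirmatory conclusion.

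**What to change.** In 2.6.3 and 2.6.4, including the sub-bullet in 2.6.4 for subjects never dosed, censor at the earlier of non-VTE death and the last date on which VTE outcome status was known. Define that date as the Day 210 date only if event status was reported as known there, and otherwise as the last complete outcome assessment, as in 2.6.1. State that a contact or registry check yielding vital status alone does not extend VTE follow-up. It would also help to say that a known status by telephone does not imply screening for asymptomatic DVT.

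No change is needed for all-cause mortality, which the current SAP analyses over the Up-to-Day 180 period only.

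The cost is a short definition and a wording change in two sections. Section 5.2.5.2 already relies on the Day 210 event status, so no new data are required. The downside is slightly shorter follow-up in two supportive analyses. The primary analysis, alpha and testing order stay as they are.

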2.6.4. Post-First Dose Observation Period

This observation period includes all data from the first dose of study drug to Day 210/EOS.

Specifically, this observation period will include all events that have occurred after first dose through Day 210 inclusive of all events after double-blind period completion/Day 180 through Day 210 as well as all events that occurred after subject had withdrew early from the double-blind period through Day 210.

All randomized subjects will be included and the imputation rule for event times for randomized subjects but never dosed described in Section 2.6.2 will also be applied for the analysis of data for this observation period. All events that occur prior to the End-of-Study date will be included in the post-first dose observation period.

Event: All efficacy events (with respect to deaths, *VTE-related deaths are counted as events for primary efficacy composite endpoint*) that occurred from the date of first dose up to the Day 210/End-of-Study[EOS] (Section 2.5) will be included in the analysis of the Post-First Dose observation period.

- Event time - The time to event is defined as the time from first dose date to the time of the first event during this observation period.
 - For randomized subjects but never dosed: The time to event will be defined as the time from randomization to the time of the event during the time in study. This imputation rule will be applied only for the ITT population.

Censoring: Subjects who do not experience an event during this observation period will be censored.

Subjects who died during this observation period will be censored as of their death date for endpoint analysis not related to death.

- Censoring time - The time to censoring is defined as the time from first dose date to the minimum (earliest) of (last contact date [up to and including Day 210 visit date = EOS date defined in Section 2.5], death date [non VTE-related deaths])
 - For randomized subjects but never dosed: The time to censoring will be defined as the time from randomization to the minimum of (last contact date [up to and including Day 210=EOS date, death date [non VTE-related deaths]]).

Examples are illustrated in Figures in the Appendix.

